### 6.4.2. Tilt-Table Test

A tilt-table test is used to evaluate the cause of unexplained fainting (syncope). A tilt-table attempts to trigger signs and symptoms like lightheadedness, dizziness, feeling faint, or feeling like blacking out while HR and BP are being monitored. If the subject has symptoms while in the upright position on the tilt-table, the part of the nervous system that controls BP and HR suddenly lowers for a short time, less blood flows to the brain, and could possibly

cause the subject to faint. The endpoint of tilt-table testing is the reproduction of symptoms along with the characteristic circulatory pattern of the indication mentioned above, namely the induction of reflex hypotension/bradycardia, orthostatic hypotension, postural orthostatic tachycardia syndrome, or psychogenic pseudosyncope. The tilt-table test will be applied until a sustained reduction of BP of  $\geq 20$  mmHg (systolic) or  $\geq 10$  mmHg (diastolic) is observed in  $\leq 3$  minutes of being tilted-up to  $\geq 60^\circ$  from a supine position, ideally between  $60^\circ$  to  $65^\circ$ . The tilt-table test should be performed following at least 12-hours of withdrawal from vasoactive medications. The tilt-table test should be performed at least 2 hours after meals and with an empty bladder. A single tilt-table retest may be performed providing the Investigator has concluded a technical problem or operational issue during the initial test impacted the results. Under these circumstances, a follow-up tilt-table test may be performed in order to appropriately evaluate the subject's orthostasis. The follow-up tilt-table test should be performed at a minimum of one hour after the initial test, and at least 7 days prior to randomization. Assessments will be performed as specified in Schedule of Study Procedures (Table 1).

#### **6.4.3. Montreal Cognitive Assessment**

The MoCA is a global cognitive screening test with favorable psychometric properties that has been shown to be more sensitive to executive impairment than the Mini-Mental State Examination. It screens 8 domains including: visuospatial/executive, naming, memory, attention, language, abstraction, delayed recall, and orientation. Assessments will be performed as specified in the Schedule of Study Procedures (Table 1). An example of the instrument is provided in [Appendix 2](#).

#### **6.4.4. Valsalva Maneuver**

The Valsalva maneuver is a breathing technique that can be used to help diagnose a problem with the autonomic nervous system (ANS). Changes in intrathoracic pressure produce autonomically modulated transient changes in HR and BP. The Valsalva maneuver will be performed as specified in the Schedule of Study Procedures (Table 1) only for subjects with PAF to confirm diagnosis.

[REDACTED]

#### **6.4.6. Efficacy Assessments**

##### **6.4.6.1. Orthostatic Hypotension Questionnaire**

The Orthostatic Hypotension Questionnaire (OHQ) is a 2-component scale made up of a 6-item symptom assessment scale referred to as OHSA and a 4-item daily activity scale referred to as the Orthostatic Hypotension Daily Activities Scale (OHDAS). The items are scored on an 11-point scale from 0 to 10, with 0 indicating no symptoms/no interference and

10 indicating the worst possible symptoms/complete interference, and the option of selecting “cannot do for other reasons.” Assessments will be performed as specified in the Schedule of Study Procedures (Table 1). An example of the instrument is provided in Appendix 2.

#### 6.4.6.2. Patient Global Impression of Change

In the PGI-C scale, subject is asked to compare their current symptoms to their symptoms at study baseline (i.e., prior to randomization) on a 5-category scale ranging from 1 (much better) to 5 (much worse). Assessments will be performed as specified in the Schedule of Study Procedures (Table 1). An example of the instrument is provided in Appendix 2.

[REDACTED]

[REDACTED]

[REDACTED]

[REDACTED]

[REDACTED]

#### 6.4.6.7. Incidence of Falls – Subject Diary

Falls in subjects with symptomatic neurogenic orthostatic hypotension are common and potentially catastrophic. They can lead to serious injuries including hip fractures or head trauma; furthermore, fear of falling can limit mobility and physical activity. Thus, incidence of subject-reported falls is being captured in a diary. Assessments will be performed as specified in the Schedule of Study Procedures (Table 1). An example of the instrument is provided in [Appendix 3](#).

[REDACTED]

[REDACTED]

[REDACTED]

[REDACTED]

[REDACTED]

[REDACTED]

[REDACTED]

[REDACTED]

[REDACTED]

**6.4.9.** [REDACTED]

[REDACTED]

[REDACTED]

[REDACTED]

[REDACTED]

[REDACTED]

[REDACTED]

[REDACTED]

[REDACTED]

[REDACTED]

[REDACTED]

## **6.4.10. Safety Assessments**

### **6.4.10.1. Columbia-Suicide Severity Rating Scale**

The C-SSRS is a tool designed to systematically assess and track suicidal AEs (suicidal behavior and suicidal ideation). The strength of this suicide classification system is in its ability to comprehensively identify suicidal events while limiting the over-identification of suicidal behavior. The C-SSRS Baseline/Screening Version will be used at Visit 1 and the C-SSRS Since Last Visit Version will be used for subsequent visits. Assessments will be performed as specified in the Schedule of Study Procedures ([Table 1](#)). An example of the instrument is provided in [Appendix 2](#).

### **6.4.10.2. Adverse Events**

Adverse events will be reviewed and recorded from signing of the informed consent through the end of follow-up. Adverse events may be observed by the study personnel or spontaneously reported by the subject.

All AEs must be recorded in the subject's CRF and, if applicable, reported as described in [Section 7](#).

The Investigator must take all therapeutic measures necessary for resolution of AEs. Any medications necessary for the treatment of an adverse event must be recorded in the subjects CRF. Refer to [Section 7](#).

Except where described above, the Investigator may prescribe medications to provide adequate supportive care. However, the Investigator should use judgment to avoid medications that may confound the interpretation of this study.

### **6.4.10.3. Medication and Medical History**

A complete medical history will be taken during the screening visit and will include evaluation visit for past and present cardiovascular, respiratory, GI, renal, hepatic, neurological, endocrine, lymphatic, hematologic, immunologic, dermatologic, psychiatric, genitourinary, substance abuse, surgical history, or any other diseases or disorders. Medical conditions will be recorded for two years prior to screening visit, along with the date of diagnosis, and any other relevant medical history that has an impact to the subject.

Medical events or conditions that arise or worsen in severity or frequency after the signing of the informed consent will be recorded as an AE.

All medications used during the 60 days prior to screening will be recorded in the source records. The only exception is drugs that were used to treat previous orthostatic hypotension; these will be recorded since the time of primary diagnosis.

### **6.4.10.4. Physical Examination**

A full physical examination at the screening visit will be performed by an appropriately qualified individual (e.g., physician, nurse practitioner, physician's assistant, or equivalent, under the supervision of a physician) and will include examination of the following: general appearance; skin; head, ears, eyes, nose, and throat; neck; cardiovascular system; respiratory system; abdomen/gastrointestinal (GI) system; extremities; lymphatic system [lymph nodes]; and nervous system).

Subsequent physical examinations, after the screening visit on Visit 2 and Visit 6, per discretion of the Investigator, can be abbreviated and symptomatic, largely focused on evaluation of AEs, if any, and any abnormalities identified on the screening visit examination.

#### **6.4.10.5. Height and Weight**

Height (in cm) and weight (in kg) will be recorded as outlined in the Schedule of Study Procedures (Table 1). Reasonable efforts will be taken to ensure the measurements for weight occur at approximately the same time each visit using the same scale and with similar clothing.

#### **6.4.10.6. Vital Signs**

The HR, SBP and DBP, RR, and body temperature will be recorded according to the Schedule of Study Procedures (Table 1).

The vital sign measurements (BP and HR) should be performed after the subject has rested sufficiently as determined by the appropriate staff. Subject position, measurement device, and arm (left vs. right) should be kept consistent throughout the study. Blood pressure will be measured using a calibrated manual or automatic BP device.

Heart rate will be recorded by palpation of the radial pulse over at least a 30-second period or by the automated BP device.

The BP and HR collected at 10 minutes supine and seated from the [REDACTED] can be used for safety vital sign assessment.

Body temperature will be measured and reported in degrees Celsius. The method used to collect temperature can be either oral or tympanic but should be consistent throughout the subject's participation.

Any vital sign outside the normal range may be repeated at the discretion of the Investigator. Collection of additional vital sign measurements for routine safety monitoring at additional time points or study days may be performed at the discretion of the Investigator, or upon request by the sponsor.

#### **6.4.10.7. Electrocardiograms**

The 12-lead ECGs will be recorded in triplicate and separated by at least 1 minute for each replicate according to the Schedule of Study Procedures (Table 1) after the subject has been resting at least 5 minutes in the seated or supine position before the first reading. The total time to conduct ECGs ideally would not exceed 15 minutes. Actual time of the assessment must be recorded for each iteration. The corrected QT interval using the Fridericia's formula (QTcF) will be used. The ECGs should be reviewed on the visit day at the site to allow for any appropriate action, if required.

#### **6.4.10.8. 24-hour Ambulatory Blood Pressure Monitoring**

Ambulatory blood pressure monitoring equipment will be provided to the subject during the screening visit. Beginning approximately 72 to 24-hours before a subject conducts Day 1 (Visit 2), and before the Day 8 and Day 22 visits, subjects will put on the 24-hour blood pressure monitoring equipment and initiate the recording. Once the 24-hour session is complete, subjects will remove and return the equipment to the research center during the next visit. During each 24-hour session, the BP monitoring device will be programmed to

automatically measure BP every 2 hours beginning at the top of the hour. During each 24-hour session, subjects should also maintain a log of their posture at the time of each BP measurement ([Appendix 4](#)). More details regarding the ambulatory monitoring will be provided in a separate manual.

#### **6.4.10.9. Laboratory Tests**

Laboratory tests will be performed as specified in Schedule of Study Procedures ([Table 1](#)).

Additional and repeat laboratory safety testing for the evaluation of abnormal results and/or AEs during the study may be performed at the discretion of the Investigator or upon request of the sponsor.

Detailed instructions and collection kits for sample collection, handling, and shipping will be provided in the laboratory manual.

##### **6.4.10.9.1. Hematology**

Hematology samples will be analyzed for the following: hematocrit and hemoglobin; red blood cell count; mean corpuscular volume; mean corpuscular hemoglobin; white blood cell count, including differential count (percent and absolute) of neutrophils, eosinophils, basophils, monocytes, lymphocytes; platelet count and HgbA1C (if applicable).

##### **6.4.10.9.2. Chemistry**

Chemistry samples will be analyzed for the following: sodium, potassium, calcium, chloride, bicarbonate, glucose, blood urea nitrogen, creatinine, eGFR, total protein, albumin, alkaline phosphatase, ALT, AST, bilirubin, lactate dehydrogenase, and creatine phosphokinase.

##### **6.4.10.9.3. Urinalysis**

Urinalysis includes determination of specific gravity; presence of blood, protein, and leukocytes; and microscopic examination of sediment, if clinically indicated.

##### **6.4.10.10. Neurological Examination**

Any abnormalities identified at the Screening Visit will be recorded as neurological medical history. Any abnormalities or symptoms reported during treatment that arise or worsen in severity or frequency will be reported as AEs.

The PI should perform a neurological exam in clinic or via telemedicine platform for remote visits (assisted as necessary by the home health nurse) as required to assess the subject's current condition and include the following exams per the PI's medical discretion.

The examination will assess the following:

- Cranial nerves (cranial nerves II-XII, excluding fundoscopic examination)
- Motor system (tone, strength, and abnormal movements)
- Sensory system (light touch, pinprick, joint position, and vibration)
- Reflexes (deep tendon reflexes and plantar responses)
- Coordination (upper and lower extremities)
- Gait (base and tandem gait)

- Station (posture and stability)

#### **6.4.10.11. Dosing Diary Dispensation and/or Collection**

On a daily basis, the subjects will record the time of study medication administration in the diary provided on Visit 2. Dosing diary with completion instructions, including study medication dosing details, will be provided to each subject. Subjects will be instructed to record daily dosing through the end of the treatment period ([Appendix 5](#)). Diary completion will be monitored for completeness at each study visit after the diary is dispensed. Subjects will be counseled on missed study medication doses and missed diary entries. Compliance with the dosing regimen will be assessed by reconciliation of used and unused study medication.

#### **6.4.10.12. Unscheduled Visit**

All sites are allowed at Investigator discretion to conduct either in clinic or remote unscheduled visits for subject safety or unexpected subject medical needs outside of the regular visit schedule. In this case, unscheduled visits are not considered protocol deviations and the Investigator is not required to obtain pre-approval from the Sponsor. Data collected during these visits may include any protocol-specified assessments which will be captured in the clinical database.

### **6.5. Concomitant Medications**

Subjects should not have changed dose, frequency or type of prescribed medication for orthostatic hypotension within 7 days prior to the randomization visit.

[REDACTED]

Stable dosing regimen is defined as the same dosage and frequency on any given day.

Subjects who are smokers will be recommended to either stop smoking (cigarettes or cannabinoids in countries where cannabinoids are permissible) at least 7 days before first dose or maintain a constant smoking habit during the entire course of the study.

#### **6.5.1. Impact of Other Medications on TD-9855**

[REDACTED]

**6.5.2. Impact of TD-9855 on Other Medications**

[REDACTED]

**6.6. Rescue Medications**

[REDACTED]

- [REDACTED]

- [REDACTED]

[REDACTED]

**6.7. Prohibitions and Restrictions**

The following are prohibited or restricted during study participation as specified:

- [REDACTED]

- [REDACTED]

- [REDACTED]

- [REDACTED]

- [REDACTED]

- [REDACTED]

- [REDACTED]

## 6.8. Discontinuation

### 6.8.1. Dose Stopping Rules

Any subject meeting 1 or more of the following stopping criteria will be required to immediately discontinue dosing with study medication and subsequently subject will be discontinued from participation in the study:

- [REDACTED]
- [REDACTED]
- [REDACTED]
- [REDACTED]

### 6.8.2. Subject Discontinuation

Any subject (or his or her legally authorized representative) may withdraw their consent to participate in the study at any time without prejudice. The Investigator must withdraw from the study any subject who requests to be withdrawn. A subject's participation in the study may be discontinued at any time at the discretion of the Investigator and in accordance with his or her clinical judgment. When possible, the tests and evaluations listed for the termination visit should be completed. If a subject withdraws before completing the study, the reason for withdrawal is to be documented on the CRF.

The sponsor will be notified of all subject withdrawals.

Reasons for which the Investigator may withdraw a subject from the study or a subject may choose to terminate participation before completion of the study include, but are not limited to, the following:

- Adverse Event
- Physician Decision
- Pregnancy
- Protocol Violation
- Withdrawal by Subject
- Other

The subject may also discontinue from the study if the study is discontinued by the Sponsor.

Subjects who discontinue study medication early because of an adverse reaction should be encouraged to continue their participation in the follow-up safety assessments. If a subject fails to return for scheduled visits, a documented effort must be made to determine the reason.

### 6.8.3. Subject Replacement

Subjects will not be replaced.

#### **6.8.4. Study Discontinuation**

The sponsor reserves the right to discontinue this study at any time for any reason.

Periodic review of unblinded safety data by an external independent data monitoring committee (Section 8.8) may lead to the board's recommendation of pausing dosing or terminating the study. In the event of premature study termination, best efforts to guarantee appropriate safety follow-up of subjects who have already been enrolled will be made and institutional review boards (IRBs) and the regulatory authorities will be informed.

#### **6.9. Pregnancy**

TD-9855 has been shown to be non-genotoxic in a standard battery of genotoxicity assays (in vitro Ames and chromosomal aberration assays and in vivo micronucleus assay in rat). TD-9855 demonstrated effects on neonatal mortality and decreased rates of pup growth in the pre- and postnatal study in rats. Based on the NOAEL in reproductive-toxicology studies in preclinical species, there exists a greater than 100x margin between exposure in preclinical species at NOAEL vs. exposure in male and female subjects at 4 weeks post stopping administration of 10mg TD-9855 dose. Thus, application of pregnancy prevention measures for 1 month post last dose of TD-9855 is sufficient to address the risk of substantial drug exposure in semen or maternal circulation.

To confirm the absence of pregnancy in female subjects of childbearing potential, urine beta human chorionic gonadotropin (bHCG) testing will be performed during specified visits, as listed in the Schedule of Study Procedures ([Table 1](#)). If the urine bHCG test is positive, a serum bHCG test must be performed. The pregnancy test must be confirmed negative for a subject to be eligible for this study unless the PI deems the test is falsely positive.

If a subject becomes pregnant while taking TD-9855, or during the 1 month after the last dose of treatment, the pregnancy must be reported to the sponsor's medical monitor (or designee) immediately (within 24-hours) by following the procedures for SAE reporting as outlined in [Section 7.4.3](#). Study drug must be discontinued for any pregnant subject still on study drug treatment. Follow-up information regarding the outcome of the pregnancy and any postnatal sequelae in the infant will be required.

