### **Inclusion Criteria:**

A subject who meets the following criteria will be eligible for study enrollment:

1. Subject is male or female and at least 30 years old.
2. Subject is female and must be nonpregnant and nonlactating. A woman of childbearing potential must have a documented negative pregnancy test at screening.

**NOTE:** A woman is considered to be of childbearing potential unless she is postmenopausal (amenorrheic for at least 2 years) or documented to be surgically sterile (bilateral tubal ligation or total hysterectomy). A female subject may be admitted to the study on the basis of a negative urine pregnancy test. If the urine bHCG (beta human chorionic gonadotropin) test is positive, a serum bHCG test must be performed. The pregnancy test must be confirmed negative for a subject to be eligible for this study.

3. During the study and for 30 days after receiving the last dose of the study drug, females of childbearing potential or males capable of fathering children must agree to use highly effective birth control measures (failure rate <1% when used

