- h. In women of childbearing potential only. First, urine beta human chorionic gonadotropin (bHCG) test will be performed and if positive, confirmation with serum bHCG test is required. The pregnancy test must be confirmed negative for a subject to be eligible for this study.

- i. [REDACTED]
- j. [REDACTED]
- k. Ambulatory blood pressure monitoring equipment will be provided to the subject during the screening visit. Beginning approximately 72 to 24-hours before a subject conducts the Day 1 (Visit 2), and before the Day 8 and Day 22 visits, subjects will put on the 24-hour blood pressure monitoring equipment and initiate the recording. Once the 24-hour session is complete, subjects will remove and return the equipment to the research center during the next visit. During each 24-hour session, the blood pressure monitoring device will be programmed to automatically measure blood pressure every 2 hours beginning at the top of the hour. During each 24-hour session, subjects should also maintain a log of their posture at the time of each blood pressure measurement. Details regarding the ambulatory monitoring will be provided in a separate manual.
- l. Study medication will be ingested in the morning at approximately the same time of day with 8 ounces of water. The exact time and day of dosing will be recorded on the mornings of study visits. Subjects should be reminded to maintain an adequate fluid intake during their scheduled visits.
- m. The assessments or procedures will be performed within 24-hours prior to subject taking the study medication (pre-dose). Following randomization and completion of study assessments, the subject will begin taking study medication on Day 2 in the morning.
- n. C-SSRS is to be completed following OHQ questionnaire from Visit 2 to Visit 6.
- o. Follow-up visit is only applicable for those subjects that do not proceed to Study 0170 and will be completed two weeks from the date of the last dose.
- p. The assessment should be performed at approximately ( $\pm 2$  hour) the same time of day on Day 1 (except Screening). Subjects should abstain from eating for at least 90mins prior to this assessment.
- q. Valsalva maneuver is to be performed for PAF subjects only if no results are available within 24 months from the date of randomization.

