### **4.3. Pregnancy and Contraception**

#### **4.3.1. Females of Childbearing Potential**

Females of childbearing potential must have documentation of a negative pregnancy test at screening and prior to dosing.

Females are considered to be not of childbearing potential if they have had a total hysterectomy and/or bilateral tubal ligation or hysteroscopic sterilization (documentation for surgeries must be provided before randomization) or are in a postmenopausal state (i.e., females who have had cessation of prior occurring menses for  $\geq 24$  months without alternative causes or females with premature ovarian failure).

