5. C-SSRS
6. Randomization via a RTSM system (after all pre-dose procedures have been completed and subject is confirmed to be eligible for the study)

The following procedures are listed in the recommended order, however flexibility for scheduling is permitted:

[REDACTED]  
[REDACTED]  
[REDACTED]  
[REDACTED]  
[REDACTED]  
[REDACTED]  
[REDACTED]  
[REDACTED]  
[REDACTED]  
[REDACTED]  
[REDACTED]  
[REDACTED]  
[REDACTED]

- 14. Vital signs
  - a. HR, SBP, and DBP
  - b. RR and body temperature
- 15. Weight (in kg)
- 16. Physical examination
- 17. Neurological examination
- 18. Pregnancy test (in women of childbearing potential only)
- 19. Blood collection
  - a. Hematology
  - b. Chemistry
- 20. Urine collection
  - a. Urinalysis

[REDACTED]

- 22. Incidence of Falls and ABPM position diaries
- 23. 24-hour ambulatory BP device collection and re-provision
- 24. Dosing and Midodrine rescue medication diaries dispensation and review of diary completion instructions
- 25. AE assessment (AEs, SAEs, AESIs)
- 26. Dispense study medication

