4. PGI-C
5. C-SSRS

The following procedures are listed in the recommended order, however flexibility for scheduling is permitted:

[REDACTED]  
[REDACTED]  
[REDACTED]  
[REDACTED]  
[REDACTED]  
[REDACTED]  
[REDACTED]  
[REDACTED]  
[REDACTED]  
[REDACTED]  
[REDACTED]  
[REDACTED]

13. Vital signs
  - a. HR, SBP, and DBP
  - b. RR and body temperature
14. Weight (in kg)
15. Physical examination
16. Neurological examination
17. 12-lead ECG (in triplicate separated by at least 1 minute for each replicate, after the subject has been resting for at least 5 minutes)
18. Pregnancy test (in women of childbearing potential only)
19. Blood collection
  - a. Hematology
  - b. Chemistry
20. Urine collection
  - a. Urinalysis

[REDACTED]  
[REDACTED]

23. Incidence of Falls and ABPM position diaries
24. Dosing and Midodrine rescue medication diaries dispensation and review of diary completion instructions
25. AE assessment (AEs, SAEs, AESIs)

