### 6.4.1. Demographic and Baseline Assessments

Demographic information to be collected will include: year of birth, sex, race, and ethnicity.

Inclusion and exclusion criteria will be assessed at screening and on Day 1 prior to randomization. Subjects will only be eligible for enrollment into the study if they meet all the applicable inclusion and none of the applicable exclusion criteria.

Each subject will be asked to provide relevant medical history (including medication history; see Section 6.4.10.3).

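### Section 6.9 lets the PI waive the confirmed-negative pregnancy test by calling it falsely positive; inclusion criterion 2, footnote h and Section 4.3.1 allow no such exception

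*Protocol*

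**What the plan says.** Section 6.9 of the protocol sets a two-step test: "If the urine bHCG test is positive, a serum bHCG test must be performed". It then makes a confirmed negative a condition of eligibility, "unless the PI deems the test is falsely positive". It does not say whether the urine or the serum test is meant, what evidence the PI needs, or whether anyone else must agree.

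The same condition stands without the exception in inclusion criterion 2 (synopsis and Section 4.1), in footnote h of Protocol Table 1 and in footnote h of SAP Table 2: "The pregnancy test must be confirmed negative for a subject to be eligible for this study". Section 4.3.1 adds: "Females of childbearing potential must have documentation of a negative pregnancy test at screening and prior to dosing". Section 6.4.1 gives the general rule: "Subjects will only be eligible for enrollment into the study if they meet all the applicable inclusion and none of the applicable exclusion criteria".

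**The concern.** One safety rule is stated in two ways. Section 6.9 is the section on pregnancy and describes the test sequence, so a site with a positive result may well turn to it. There it finds a permission that the inclusion criteria do not give. A site that acts on it can enrol a woman who does not satisfy the eligibility rules, and the resulting deviation is one that the protocol itself invited.

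The underlying stake is fetal exposure. Section 6.9 reports effects on neonatal mortality and pup growth in rats. Elsewhere the protocol bounds clinical discretion: exclusion criterion 1 brings in the medical monitor and lists conditions for diabetes, and exclusion criterion 9 relies on an ophthalmologist for treated closed angle glaucoma. The waiver in Section 6.9 has no comparable limit.

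**Working it through.** No figure in the plan bears on this point, so the check compares the texts.

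**Where the exception appears**

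- Section 6.9: confirmed negative required, with a PI exception.
- Inclusion criterion 2, synopsis and Section 4.1: confirmed negative required, no exception; also a documented negative at screening.
- Footnote h, Protocol Table 1 and SAP Table 2: confirmed negative required, no exception.
- Section 4.3.1: documented negative at screening and before dosing, no exception.
- Section 6.4.1: silent on pregnancy testing. It matters only because it requires every applicable inclusion criterion to be met.

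The exception therefore stands in one place only.

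**What the exception can do**

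1. Urine negative: the requirement is met and no exception is needed.
2. Urine positive, serum negative: the serum result is the confirmed negative. Again no exception is needed.
3. Urine positive, serum not negative: the strict rule makes the woman ineligible. This is the only outcome of the completed sequence in which an exception could matter.
4. Urine positive, serum not done: this breaches Section 6.9 itself, which makes the serum test mandatory, so it is not a route that the clause opens.

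If the clause means the urine test, shown false by a negative serum result, it only restates case 2 and is redundant. If it means the confirmed result, it acts in case 3 and conflicts with inclusion criterion 2 and Section 4.3.1. The second reading is the more literal one, because the exception qualifies the confirmed-negative condition and comes after the serum step. On neither reading does the clause do useful work that agrees with the other sections.

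**Which rule is broken depends on timing**

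- Waiver used at screening: the woman lacks the documented screening negative that inclusion criterion 2 and Section 4.3.1 require. The Day 1 test is then a second check before dosing.
- Waiver used on Day 1 after a negative screening test: Section 4.3.1 is breached. Inclusion criterion 2 is breached too if its note, which names no visit, is read as covering Day 1.

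**Caveat on possible duration**

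After Day 1 the next scheduled pregnancy test is at Visit 6 / Early Termination (Section 6.3.6); Sections 6.3.3 to 6.3.5 list none. The first dose is on Day 2, with one dose a day. Counting the dose on the morning of the visit, doses up to that test = visit day − 2 + 1:

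- Day 26: 26 − 2 + 1 = 25
- Day 29: 29 − 2 + 1 = 28
- Day 32: 32 − 2 + 1 = 31

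This is how long a missed case could go without a scheduled test if the woman stayed on treatment. It is not an expected exposure.

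**The case against.** The strongest reply is that Section 6.9 does not decide eligibility on its own. Section 6.4.1 requires all inclusion criteria to be met, Section 6.3.2 opens Day 1 with an eligibility review, and randomisation there comes only "after all pre-dose procedures have been completed and subject is confirmed to be eligible for the study". Section 4.3.1 separately asks for a documented negative before dosing. A reader might infer that Section 6.9 by itself admits a pregnant woman to treatment. The documents do not support that, because the waiver would have to be used and Section 4.3.1 overlooked as well. This part of the reply stands and limits the consequence. It does not remove the conflict between the sections.

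A second reply is that the clause means only a false-positive urine test. That reading is available, and on it nothing changes. It is also a reason to delete the clause.

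A third reply is that the clause may be there for a non-pregnant woman with a false-positive serum result. That is a fair purpose, but the text gives no way to establish such a result, and inclusion criterion 2 excludes her in any case.

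Two further inferences should be resisted. The count of 25 to 31 doses could be read as a likely exposure. It needs a serum result that is not negative in a woman who is in fact pregnant, a mistaken PI judgement, a missed Section 4.3.1 and no unscheduled testing, although Sections 6.4 and 6.4.10.12 leave room for extra tests and visits. Nor does the margin of more than 100-fold in Section 6.9, which refers to 4 weeks after stopping, show that the margin during dosing is poor. The toxicology and clinical pharmacokinetic sections are redacted, so that margin cannot be judged here.

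**Conclusion.** The inconsistency is real and lies in the current text. Section 6.9 allows an unbounded PI exception to a requirement that inclusion criterion 2, both footnotes h and Section 4.3.1 state without one. Because a positive urine test already leads to serum testing, the exception is either redundant or an override of a serum result that is not negative.

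The size is small. It concerns women of childbearing potential with a positive urine test, and the documents give no number for them. Fetal exposure would need at least two failures together. Alpha, power and bias are not affected. The correction is still worth making, because the rule protects subjects and one clause settles it. The conclusion rests on taking a negative serum result after a positive urine result as the confirmed negative, which is how the test sequence in inclusion criterion 2, footnote h and Section 6.9 reads.

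**What to change.** In Section 6.9, delete the exception so that the sentence matches inclusion criterion 2 and footnote h. Alternatively limit it: a positive urine bHCG may be treated as falsely positive only if the serum bHCG is negative, and a subject whose serum test is not negative is ineligible. If the sponsor wants a route for a genuine false-positive serum result, it should define one procedure and state it identically in Section 6.9, inclusion criterion 2, footnote h and Section 4.3.1.

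Deleting or limiting the clause changes one sentence. The SAP already carries the strict rule, and the serum test is already mandatory. There are two small costs. A rare non-pregnant woman with a false-positive serum result is excluded, as inclusion criterion 2 already requires. And a positive urine test on Day 1 means waiting for the serum result; if the wait exceeds the 24-hour pre-dose window in footnote m, that subject's pre-dose assessments, including the baseline OHQ, may have to be repeated.
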